**Table 8.1-1 Schedule of events**

Events	Visit 1 Screening	Visit 2 First usage visit	Visits 3-4 Second and third usage visit
Informed consent	X		
Demographics	X		
Medical/surgical history	X		
History of nicotine use	X		
Inclusion/exclusion criteria	X	X 	
Brief oral examination	X	X	X
Salivary secretion rate	X		
Salivary buffer capacity	X	X	X
Pregnancy test 	X	X 	X 
Baseline symptoms	X	X	
Prior and concomitant medications		X	
Randomization		X	
Administration of IP		X	X
Plaque acidogenicity 		X	X
Oral mucosa effects		X	X
VAS question		X	X
Collection of saliva		X	X
AEs		X	X

Confirmation of eligibility criteria.

Only women of childbearing potential.

Only at the discretion of the Investigator on Visits 2-4.

Assessed at 0, 2, 5, 10, 15, 30, and 45 minutes.

## 8.2 Rationale for study design

This is an open-label, randomized, 3-way crossover, single administration study designed to assess the effects on dental plaque acidogenicity after using Dry 3 mg NPs, [REDACTED] in current daily users of NP or tobacco-based snus.

Randomization will be used to minimize bias in the assignment of subjects to an IP use sequence, increasing the likelihood that known and unknown subject attributes (e.g., demographic and baseline characteristics) will be evenly balanced.

A crossover design was chosen to yield a more efficient evaluation of NPs than a parallel study design, as fewer subjects are required since each subject will serve as their own control. To avoid carry-over effects, subjects will abstain from nicotine products (including smoking) for at least 1 hour prior to each IP use visit (Visits 2-4). Additionally, there will be at least three days between each of the three usage visits with single administration to allow for accurate assessment of dental plaque acidogenicity.

## 9 STUDY POPULATION

Prospective approvals of protocol deviations from eligibility criteria, also known as protocol waivers or exemptions, are not permitted.

### 9.1 Recruitment

Participants will be recruited through locally distributed posters, targeting personnel and students at the Institute of Odontology in Gothenburg, Sweden. The recruitment materials will be created using advertising texts approved by the independent ethics committee (IEC).

### 9.2 Screening and enrolment log

The PI must keep a record of all screened subjects even if they were not subsequently included in the study. This information is necessary to verify that subjects were selected without bias. The reason for screening failure should be stated for all subjects that were screened but not included. The reason for withdrawal should be stated for all subjects that were included but did not complete the study.

A screening number will be allocated to each subject in connection with the informed consent process at the screening visit (Visit 1). The screening number will be manually assigned and recorded in the case report form (CRF). This number will allow identification of subjects irrespective of their eligibility for the study.

Subjects included and randomized will be assigned a randomization number (101, 102 *etc.*).

### 9.3 Number of subjects

Approximately 20 subjects will be screened with the aim of achieving 12 randomized and fully evaluable subjects. A fully evaluable subject is defined as one who has used the IPs and completed all study visits. An effort will be made to randomize at least 3 female subjects (25%).

For replacements of subjects who discontinue from the study, see Section 9.8.3.

### 9.4 Inclusion criteria

For inclusion in the study, the subjects must fulfil the following criteria:

1. Willing and able to give written informed consent for participation in the study.
2. Subjects who have used NPs or tobacco-based snus for  $\geq 1$  year, with a minimum weekly consumption of 3 cans.
3. Healthy male or female subject aged  $\geq 21$  to  $\leq 55$  years.
4. Normal stimulated salivary secretion rate ( $>0.7$  mL/min).
5. At least 24 own teeth remaining and overall good oral health, as judged by the Investigator.
6. Women of child-bearing potential must practice abstinence from heterosexual intercourse (only allowed when this is the preferred and usual lifestyle of the subject) or must agree to use a highly effective method of contraception with a failure rate of

<1% to prevent pregnancy for the duration of the study. The following are considered highly effective methods of contraception:

- combined (estrogen and progestogen containing) hormonal contraception associated with inhibition of ovulation (oral, intravaginal, transdermal),
- progestogen-only hormonal contraception associated with inhibition of ovulation (oral, injectable, implantable),
- intrauterine device or intrauterine hormone-releasing system.

## 9.5 Exclusion criteria

Subjects must not enter the study if any of the following exclusion criteria are fulfilled:

1. A history of diagnosed hypertension or any cardiovascular disease, or ongoing manifestations of hypertension or any cardiovascular disease as judged by the Investigator.
2. Any surgical or medical condition, including abnormal salivation (also pharmaceutically induced), or history thereof, which, in the judgment of the Investigator, might interfere with the absorption, distribution, metabolism or excretion of the IP or may either put the subject at risk because of participation in the study, influence the results, or the subject's ability to participate in the study.
3. Subjects who are pregnant, breastfeeding, or intend to become pregnant during the course of the study.
4. A history of diagnosed severe allergy/hypersensitivity or ongoing manifestations of severe allergy/hypersensitivity to aroma compounds (including fragrances and/or flavorings), as judged by the Investigator.
5. Subjects with severe oral conditions such as open caries lesions, severe periodontal health, lesions in soft tissues (apart from oral mucosal lesions related to the use of snus), or extensive prosthetic work (e.g., several implants, partial denture, dental veneers).
6. Any planned major surgery within the duration of the study.
7. Current or history of alcohol abuse and/or use of anabolic steroids or drugs of abuse, as judged by the Investigator.
8. Antibiotic use  $\leq$ 4 weeks prior to the screening period.
9. Subjects who intend to change their nicotine consumption habit, including the intention to stop using nicotine products, within the next 3 months of the screening visit, as judged by the Investigator.
10. Subjects undergoing other dental treatment during the study period.
11. The Investigator considers the subject unlikely to comply with study procedures, restrictions, and requirements.

## 9.6 Restrictions during the study

Subjects must be willing to comply with the restrictions as outlined in Sections 9.6.1 and 9.6.2.

#### 9.6.1 ***General restrictions***

1. **Tooth cleaning and toothbrushing:** Subjects shall refrain from approximal tooth cleaning for 24 hours and toothbrushing for 12 hours prior to the usage visits (Visits 2-4).
2. **Contraception requirements:** Women of childbearing potential are expected to use contraceptive methods in accordance with inclusion criterion #6 or practice abstinence from heterosexual intercourse (if this is their consistent practice) during the study.
3. **Tobacco/nicotine products:** Subjects shall abstain from all other nicotine products 1 hour prior to the usage visits (Visits 2-4).
4. **Mouth-related procedures:** Subjects shall abstain from eating, drinking, or conducting any other mouth-related procedure for 1 hour prior to IP use, during IP use, and for 30 min after IP removal (Visits 2-4).
5. **Participation in other clinical studies:** Subjects are not allowed to participate in any other clinical studies or use antibiotics during the study period (Visits 1-4).

#### 9.6.2 ***Prior and concomitant therapy***

The use of antibiotics is not allowed from the screening visit (Visit 1) to the last usage visit (Visit 4) in accordance with exclusion criterion #8. Subjects undergoing other dental treatment during the study period will be excluded from the study according to exclusion criterion #10. There will be no other restrictions concerning concomitant medications or therapies, as long as the subject is on a stable course of medication from the screening visit to the last usage visit (Visit 4). Prescribed medications taken *pro re nata* may be a reason for exclusion as judged by the Investigator if they affect the subject's general condition or salivation.

### 9.7 **Screen failures**

Screen failures are defined as subjects who consent to participate in the clinical study but do not fulfill all eligibility criteria and are not subsequently included in the study. A minimal set of screen failure information is required to ensure transparent reporting of screen failure subjects. Minimal information includes documentation of signed and dated informed consent form (ICF) and reason(s) for screening failure.

Rescreening can be performed if any of the following were reasons for screening failure or non-randomization (as judged by the Investigator):

- Practical reasons
- Non-significant medical conditions (*e.g.*, influenza, nasopharyngitis)
- Reserve subjects

For subjects who are re-screened, a new screening number will be assigned and a new, signed ICF must be collected.

## 9.8 Subject withdrawal

### 9.8.1 *General withdrawal criteria*

Subjects are free to discontinue their participation in the study at any time and for whatever reason without affecting their right to an appropriate follow-up investigation or their future care. If possible, the reason for withdrawal of consent should be documented.

Subjects may be discontinued from the study at any time at the discretion of the Investigator.

Reasons for discontinuation can include:

1. AE (as judged by the Investigator and/or Sponsor)
2. Logistical problem
3. Lost to follow-up
4. Non-compliance with study schedule and restrictions
5. Pregnancy
6. Withdrawal of consent
7. Other

### 9.8.2 *Procedures for discontinuation of a subject from the study*

A subject who prematurely discontinues participation in the study will always be asked about the reason(s) for discontinuation and the presence of any AEs. Any ongoing AEs will be followed up as described in Section 11.6.10.

The primary reason for discontinuation/early withdrawal must be specified in the CRF. If the reason for discontinuation was an AE, the AE must be specified in the CRF.

### 9.8.3 *Subject replacement*

Subjects who are prematurely withdrawn prior to the start of IP use may be replaced at the discretion of the Sponsor.

## 9.9 Randomization

At Visit 2, subjects will be randomized to one of 3 use sequences. The following sequences will be randomized:

Sequence 1: A B C

Sequence 2: B C A

Sequence 3: C A B

Where

A = Dry 3 mg NP (reference)

B = Prototype A Dry 3 mg NP [REDACTED]

C = Prototype B Dry 3 mg NP [REDACTED]

As this is an open-label study, the IP use sequence to which each subject is allocated will be recorded in the CRF.

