## 8 STUDY DESIGN

### 8.1 Overall study design and schedule of events

This is an open-label, randomized, 3-way crossover, single administration study designed to assess the effects on dental plaque acidogenicity after using Dry 3 mg NPs, [REDACTED] in current daily users of NP or tobacco-based snus. The IPs are one Dry 3 mg NP (reference product) and two prototype products [REDACTED]. [REDACTED]. [REDACTED]

The study will include 12 randomized and fully evaluable subjects. Healthy male and female subjects aged  $\geq 21$ - $\leq 55$  years who have used NP or tobacco-based snus for  $\geq 1$  year, with a minimum weekly consumption of 3 cans, may be eligible for participation. An effort will be made to randomize at least 3 female subjects (25%).

The subjects will visit the test laboratory on four occasions, with at least three days between each visit. Each visit will last approximately 1.5 hours. Consequently, each subject is expected to participate in the study for about two weeks, excluding the screening period.

The subjects will report to the test laboratory for a screening visit (Visit 1), which will take place within four weeks prior to the first usage visit (Visit 2). This screening visit will involve an eligibility check, including evaluations of smoking and oral tobacco/nicotine use, a brief oral examination, urine pregnancy testing (for women of childbearing potential only), and collection of medical history. Additionally, the salivary secretion rate, buffer capacity, and the number of cariogenic bacteria (*Streptococcus mutans* and lactobacilli) will be assessed.

Before each usage visit (Visits 2-4), scheduled at the same time of day for each subject, the subjects will refrain from approximal tooth cleaning for 24 hours and toothbrushing for 12 hours prior to the visits. Additionally, subjects will be instructed not to eat, drink, chew gum, use nicotine-containing products (including smoking), or engage in any other mouth-related procedures 1 hour before the visits. Subjects will use their regular toothbrush, which may be manual or electric, throughout the study. Urinary pregnancy tests may be conducted at Visits 2-4 for women of childbearing potential.

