On the first usage visit (Visit 2), subjects will be randomized to one of three usage sequences. During each usage visit (Visits 2-4), the subjects will place the IP in their upper vestibulum, where they normally place their pouches, using their fingers. The IP will be kept in place for 45 minutes. Dental plaque acidogenicity will be assessed by measuring pH in the plaque at four different locations before placement (baseline), and at 2, 5, 10, 15, 20, 30, and 45 minutes afterwards. All pH assessments will be performed on the same side as the IP placement.

The salivary buffer capacity will be assessed at baseline (0 minutes), and at 15, 30, and 45 minutes. Unstimulated saliva will be collected at each time point.

The effects on the oral mucosa from the usage of each IP will be assessed before (baseline) and after 45 minutes of usage. The effects, in the form of redness and mechanical irritation, will be graded as: no effect, mild effect, and severe effect. Photos will be taken before and after the usage of each IP to enable a more detailed comparison on the effects.

The subjective salivary stimulation effect of each IP will be evaluated after 30 minutes of use using a 100 mm VAS, anchored with “no effect” to “extremely large effect”.

AEs will be collected by subject interview and those spontaneously reported by the subjects from the first usage visit (Visit 2) to the last usage visit (Visit 4).

See Table 8.1-1 for the schedule of events applicable for each visit. Study assessments are described in Section 11.

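### The three cyclic sequences give each product one fixed predecessor; all six orders fit the same 12 subjects and reduce exposure to unequal carry-over at no cost in precision

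*Protocol*

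**What the plan says.** Protocol section 8.1 describes the design: "This is an open-label, randomized, 3-way crossover, single administration study". It adds that at the first usage visit "subjects will be randomized to one of three usage sequences", and the synopsis says the same. Section 9.9 repeats this, "At Visit 2, subjects will be randomized to one of 3 use sequences", and names the sequences: "Sequence 1: A B C", "Sequence 2: B C A" and "Sequence 3: C A B". Its key makes code A the reference and reads "B = Prototype A Dry 3 mg NP" for the second code; code C is Prototype B. The target number is in 8.1: "The study will include 12 randomized and fully evaluable subjects". No allocation ratio is given.

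Section 8.2 names carry-over as something to avoid. It relies on one hour without nicotine before each usage visit and on a gap of three days or more between usage visits. It does not say why three of the six possible orders are used. Section 17.1 plans a two-way ANOVA with Tukey's test and names no carry-over term.

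**The concern.** In a three-period crossover, a cyclic square balances product against period but not product against preceding product. Here the reference is only ever preceded by Prototype B, Prototype A only by the reference, and Prototype B only by Prototype A. The orders ACB, BAC and CBA never occur.

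Two things follow. If the products leave different residual effects, an analysis without a carry-over term passes part of that difference into the product contrasts. If someone later wants to check for this, the design separates product from carry-over only with a large loss of precision. For example, a residual from Prototype B would fall on the reference alone and move both prototype-versus-reference comparisons in the same direction.

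**Working it through.** Section 17.2 states 12 subjects without a calculation, SD, effect size or power. There is no figure of the plan's own to reproduce, and results are given in units of the within-subject SD, σ.

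**Inputs.** Three periods, three products and the three sequences (9.9); 12 subjects (8.1). Assumptions: equal allocation (4 per sequence, or 2 per order with six orders); fixed subject and period effects; additive first-order carry-over λ_A, λ_B, λ_C, by sequence code.

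**1. Predecessors.** With the three sequences, the only transitions are A→B, B→C and C→A, each in 8 of the 24 period-2 and period-3 visits. With six orders, each of the six ordered pairs occurs 4 times.

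**2. Bias without a carry-over term.** Every subject receives each product once and periods are balanced, so the contrast is a difference of product means.
- Three sequences: the means of A, B and C carry (2/3)λ_C, (2/3)λ_A and (2/3)λ_B. Hence bias(B−A) = (2/3)(λ_A−λ_C), bias(C−A) = (2/3)(λ_B−λ_C) and bias(C−B) = (2/3)(λ_B−λ_A).
- Six orders: the means carry (1/3)(λ_B+λ_C), (1/3)(λ_A+λ_C) and (1/3)(λ_A+λ_B). Hence bias(B−A) = (1/3)(λ_A−λ_B), bias(C−A) = (1/3)(λ_A−λ_C) and bias(C−B) = (1/3)(λ_B−λ_C).

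In both designs the three contrasts involve all three pairwise differences in λ, so the largest of the three biases is exactly halved. If only Prototype B (code C) leaves a residual λ, the biases of B−A and C−A are −0.67λ and −0.67λ with three sequences, and 0 and −0.33λ with six orders.

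**3. Variance.** After subjects and periods are eliminated, the information on product contrasts is 12, so the unadjusted variance is 2σ²/12 = 0.167σ² in both designs. The information on carry-over contrasts is 8 − 4/3 = 20/3 in both. The product-by-carry-over term has size 8 with three sequences and 4 with six orders. Adjusted information is therefore:
- three sequences: 12 − 8²/(20/3) = 12 − 9.6 = 2.4, variance 2σ²/2.4 = 0.833σ²;
- six orders: 12 − 4²/(20/3) = 12 − 2.4 = 9.6, variance 2σ²/9.6 = 0.208σ².

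A direct least-squares calculation on the full design matrices gives the same values. The detectable differences and power use the noncentral t, two-sided 0.05 per comparison, without the Tukey penalty:

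| | Three sequences | Six orders |
|---|---|---|
| Variance, no carry-over term | 0.167σ² | 0.167σ² |
| Variance, carry-over fitted | 0.833σ² (×5) | 0.208σ² (×1.25) |
| Detectable at 80% power, unadjusted (20 df) | 1.20σ | 1.20σ |
| Detectable at 80% power, adjusted (18 df) | 2.70σ | 1.35σ |
| Power at 1.20σ, adjusted | 24% | 70% |

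**4. Cost.** Subjects (12), usage visits (36) and residual degrees of freedom do not change. With 11 completers the unadjusted variance is also equal, at 0.183σ².

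**The case against.** The strongest reply is that carry-over is dealt with by the interval, and that the documents' own facts suggest it is small. Each exposure is one pouch for 45 minutes, followed by three days or more. Subjects are daily users who need abstain for only an hour beforehand, so what last touched the mouth is more likely their usual product than a study pouch. Plaque pH and buffer capacity have a new baseline at every usage visit. All of this stands, and it limits the practical weight of the point. It does not explain the choice of three orders over six, and the protocol gives no figure for the size of any carry-over.

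Several stronger readings are tempting but are not supported:
- **That six orders remove the problem.** An unadjusted model keeps a coefficient of 1/3. Because the pair of λ values in each contrast changes, one particular contrast could even be worse for some patterns; it is the worst of the three that halves.
- **That the planned analysis would become more precise.** The gap between 0.833 and 0.208 appears only if carry-over is fitted, and 17.1 names no such term.
- **That learning on the VAS biases the comparison.** Learning over visits is a period effect, which the cyclic square balances when allocation is equal.
- **That the codes would reverse the findings.** Confusing codes B and C would exchange the two prototypes' results, not reverse them. Section 9.9 prints the key, and under 10.2 the containers carry identification numbers.
- **That the groups will be unequal.** The protocol does not state the allocation method, and 10.2 and 10.4 refer to a prepared list.

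**Conclusion.** The point holds as a missed, cost-free safeguard in a design choice that the protocol itself fixes. It is not evidence that the trial's comparisons will be biased. The three cyclic orders expose unadjusted contrasts to unequal carry-over with coefficient 2/3 and make an adjusted check five times as variable. Six orders reduce these to 1/3 and 1.25 times, with identical unadjusted precision. The figures rest on equal allocation, additive first-order carry-over and 12 completers. The size of any actual bias depends on differences between the λ values, which the documents do not give and which are probably small.

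**What to change.** In section 9.9, replace the three sequences with all six orders (ABC, BCA, CAB, ACB, BAC, CBA), 2 subjects per order, and align the wording in 8.1 and the synopsis. Do this before the randomization list and container labels are issued. Add a sensitivity analysis of the product contrasts with a first-order carry-over term and leave the main analysis without one.

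The cost is a new list and labels if these already exist, with no added subjects or visits and no loss of unadjusted precision. The sensitivity analysis alone bears the 25% increase in variance.

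For clarity only, and optional: rename the sequence codes, for example R, PA and PB, since code B now stands for Prototype A and code C for Prototype B.

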## 10 INVESTIGATIONAL PRODUCTS

The IPs are supplied by Swedish Match.

### 10.1 Identity of investigational products

The IPs that will be used in the study are detailed in Table 10.1-1.

**Table 10.1-1 Identity of IPs and nicotine contents**

IP	Nicotine content
NP Dry	3 mg nicotine/pouch
NP Dry prototype A [REDACTED]	3 mg nicotine/pouch
NP Dry prototype B [REDACTED]	3 mg nicotine/pouch
[REDACTED]	

### 10.2 Manufacturing, packaging, and labeling

All IPs are manufactured and packaged by Swedish Match in compliance with Swedish food production laws. Production sites and batch IDs for the IPs will be documented in the trial master file (TMF).

IPs will be transferred from the original container and individually packaged in identical sealed, food-approved test containers at the Swedish Match analytical laboratory. The containers will be labeled with unique identification numbers by Swedish Match in accordance with the randomization list. IPs will be shipped by Swedish Match directly to the test laboratory (Department of Cariology, Institute of Odontology, Gothenburg, Sweden).

### 10.3 Conditions for storage

All IPs will be stored at room temperature (20-25 °C) in an access-restricted storage area at the Department of Cariology.

### 10.4 Preparation and accountability

The IPs will be dispensed according to the randomization list by the site personnel. The Investigator will maintain a storage and accountability log, as well as a dispensing log, detailing the dates and quantities of study IPs received and used by each subject, as well as any IPs destroyed at the end of the study.

